7.2 PARTICIPANT DISCONTINUATION/WITHDRAWAL FROM THE STUDY

Participants are free to withdraw from participation in the study at any time upon request.

An investigator may discontinue a participant from the study for the following reasons:

- Significant study intervention non-compliance, unless varying compliance is an aspect of the study objectives
- Lost-to-follow up; unable to contact subject (see **Section 7.3, Lost to Follow-Up**)
- Any event or medical condition or situation occurs such that continued collection of follow-up study data would not be in the best interest of the participant or might require an additional treatment that would confound the interpretation of the study

- The participant meets an exclusion criterion (either newly developed or not previously recognized) that precludes further study participation

The reason for participant discontinuation or withdrawal from the study will be recorded. Subjects who sign the informed consent form and are randomized but do not receive the study intervention may be replaced. Subjects who sign the informed consent form, and are randomized and receive the study intervention, and subsequently withdraw, or are discontinued from the study, will not be replaced.

7.3 LOST TO FOLLOW-UP

A participant will be considered lost to follow-up if he or she fails to return for 1 scheduled visit and study staff are unable to contact the participant after at least 3 attempts.

The following actions must be taken if a participant fails to return for a required study visit:

- The site will attempt to contact the participant, reschedule the missed visit within 1 week, counsel the participant on the importance of maintaining the assigned visit schedule and ascertain if the participant wishes to and/or should continue in the study
- Before a participant is deemed lost to follow-up, the investigator or designee will make every effort to regain contact with the participant (where possible, 3 telephone calls and, if necessary, a certified letter to the participant's last known mailing address or local equivalent methods).
- Should the participant continue to be unreachable, he or she will be considered to have withdrawn from the study with a primary reason of lost to follow-up.

8 STUDY ASSESSMENTS AND PROCEDURES

8.1 ENDPOINT AND OTHER NON-SAFETY ASSESSMENTS

The study involves assessing participants at baseline, post-intervention, and 3-month follow-up. The participant will be screened for eligibility after consenting. They will fill out demographic questionnaires and MRI screening form to determine their eligibility. Next, they will undergo behavioral, cognitive, and brain assessments by trained research staff and/or MRI technician. All non-brain assessments will be conducted at PI's lab for all participants to decrease variability. All brain assessments will be conducted at Barrow Neurological Institute for all participants to decrease variability.

Below is a list and description of the assessments:

- **Performance-based assessments**
Cognitive assessments – N-Back working memory is a memory performance test
- **Administration of questionnaires, interviews**
Behavioral assessments – Emotional Regulation Questionnaire assesses emotion regulation, Five Facet Mindfulness Questionnaire assesses mindfulness, Subjective Cognitive Decline questionnaire assesses subjective report of cognitive decline
- **Imaging assessments**
MRI Scan – provides images of brain structure and function

8.2 SAFETY ASSESSMENTS

Based on the NIH Protocol Template for Behavioral and Social Sciences Research

N/A

8.3 ADVERSE EVENTS AND SERIOUS ADVERSE EVENTS

8.3.1 DEFINITION OF ADVERSE EVENTS

This protocol uses the definition of adverse event from 21 CFR 312.32 (a): any untoward medical occurrence associated with the use of an intervention in humans, ***whether or not considered intervention-related.***

8.3.2 DEFINITION OF SERIOUS ADVERSE EVENTS

This protocol uses the definition of serious adverse event includes: (a) Death; (b) Hospitalization (initial or prolonged); (c) Life-threatening condition; (d) Disability or Permanent Damage; (e) Other Serious (Important Medical Events).

8.3.3 CLASSIFICATION OF AN ADVERSE EVENT

8.3.3.1 SEVERITY OF EVENT

For adverse events (AEs) not included in the protocol defined grading system, the following guidelines will be used to describe severity.

- **Mild** – Events require minimal or no treatment and do not interfere with the participant's daily activities.
- **Moderate** – Events result in a low level of inconvenience or concern with the therapeutic measures. Moderate events may cause some interference with functioning.
- **Severe** – Events interrupt a participant's usual daily activity and may require systemic drug therapy or other treatment. Severe events are usually potentially life-threatening or incapacitating. Of note, the term "severe" does not necessarily equate to "serious".

8.3.3.2 RELATIONSHIP TO STUDY INTERVENTION/EXPERIMENTAL MANIPULATION

All adverse events (AEs) will have their relationship to study procedures, including the intervention, assessed by an appropriately-trained clinician based on temporal relationship and his/her clinical judgment. The degree of certainty about causality will be graded using the categories below.

- **Related** – The AE is known to occur with the study procedures, there is a reasonable possibility that the study procedures caused the AE, or there is a temporal relationship between the study

procedures and the event. Reasonable possibility means that there is evidence to suggest a causal relationship between the study procedures and the AE.

- **Not Related** – There is not a reasonable possibility that the study procedures caused the event, there is no temporal relationship between the study procedures and event onset, or an alternate etiology has been established.

8.3.3.3 EXPECTEDNESS

A clinician with appropriate expertise in medical care will be responsible for determining whether an adverse event (AE) is expected or unexpected. An AE will be considered unexpected if the nature, severity, or frequency of the event is not consistent with the risk information previously described for the study procedures.

8.3.4 TIME PERIOD AND FREQUENCY FOR EVENT ASSESSMENT AND FOLLOW-UP

The occurrence of an adverse event (AE) or serious adverse event (SAE) may come to the attention of study personnel during study visits and interviews of a study participant presenting for medical care, or upon review by a study monitor.

All AEs, not otherwise precluded per the protocol, will be captured on the appropriate case report form (CRF). Information to be collected includes event description, time of onset, clinician's assessment of severity, relationship to study procedures (assessed only by those with the training and authority to make a diagnosis), and time of resolution/stabilization of the event. All AEs occurring while on study will be documented appropriately regardless of relationship. All AEs will be followed to adequate resolution.

Any medical or psychiatric condition that is present at the time that the participant is screened will be considered as baseline and not reported as an AE. However, if the study participant's condition deteriorates at any time during the study, it will be recorded as an AE.

Changes in the severity of an AE will be documented to allow an assessment of the duration of the event at each level of severity to be performed. Documentation of onset and duration of each episode will be maintained for AEs characterized as intermittent.

PI will record events with start dates occurring any time after informed consent is obtained until 7 (for non-serious AEs) or 30 days (for SAEs) after the last day of study participation. At each study visit, the investigator will inquire about the occurrence of AE/SAEs since the last visit. Events will be followed for outcome information until resolution or stabilization.

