9.3 POPULATIONS FOR ANALYSES

The analysis population will be Modified Intention-to-Treat Analysis Population. Specifically, these participants are those who completed the full-dose of the intervention (10 sessions) and have complete and usable data for the primary endpoints.

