9.4.4 SAFETY ANALYSES

N/A

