9.4.8 TABULATION OF INDIVIDUAL PARTICIPANT DATA

Individual participant data will not be tabulated as the goal of the study is to examine group effects.

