10.1.6 SAFETY OVERSIGHT

Safety oversight will be under the direction of a Data and Safety Monitoring Board (DSMB) composed of individuals with the appropriate expertise, including clinical trials and intervention. Members of the DSMB will be independent from the study conduct and free of conflict of interest. The DSMB will meet at least semiannually to assess safety and efficacy data from each arm of the study. The DSMB will operate under

the rules of an approved charter that will be written and reviewed at the organizational meeting of the DSMB. At this time, each data element that the DSMB needs to assess will be clearly defined. The DSMB will provide its input to NCCIH via annual report.

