10.1.11 PUBLICATION AND DATA SHARING POLICY

This study will be conducted in accordance with the following publication and data sharing policies and regulations:

National Institutes of Health (NIH) Public Access Policy, which ensures that the public has access to the published results of NIH funded research. It requires scientists to submit final peer-reviewed journal manuscripts that arise from NIH funds to the digital archive PubMed Central upon acceptance for publication.

This study will comply with the NIH Data Sharing Policy and Policy on the Dissemination of NIH-Funded Clinical Trial Information and the Clinical Trials Registration and Results Information Submission rule. As such, this trial will be registered at ClinicalTrials.gov, and results information from this trial will be submitted to ClinicalTrials.gov. In addition, every attempt will be made to publish results in peer-reviewed journals. Data from this study may be requested from other researchers 10 years after the completion of the primary endpoint by contacting PI [name]. Considerations for ensuring confidentiality of these shared data are described in Section 10.1.3.

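### No by-arm harms summary and no safety population are pre-specified, and the only defined analysis set leaves out anyone who stopped early because of an adverse event

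*Combined protocol and SAP*

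**What the plan says.** **Collection.** The schedule of activities (1.3) marks adverse event reporting at every visit from Visit 1 to Visit 13. Section 8.3.4 states: "At each study visit, the investigator will inquire about the occurrence of AE/SAEs since the last visit". It covers everyone and every event: "All AEs occurring while on study will be documented appropriately regardless of relationship". Recording starts at consent and runs "until 7 (for non-serious AEs) or 30 days (for SAEs) after the last day of study participation". Severity, relationship to study procedures, onset and resolution are captured (8.3.3, 8.3.4), and the reason for stopping the intervention is recorded (7.1).

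**Oversight.** Section 10.1.6 states: "The DSMB will meet at least semiannually to assess safety and efficacy data from each arm of the study".

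**Analysis.** Under "9.4.4 SAFETY ANALYSES" the whole content is N/A. Section 9.3 defines one population, named modified intention-to-treat: "these participants are those who completed the full-dose of the intervention (10 sessions) and have complete and usable data for the primary endpoints". No safety or all-randomised population appears anywhere. Section 9.4.8 rules out listings: "Individual participant data will not be tabulated as the goal of the study is to examine group effects".

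**The concern.** The plan gathers what a harms table needs and then plans no table. Three places presuppose a summary that the statistical section does not supply:

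- 8.3.4 wants severity changes documented so that time spent at each severity level can be assessed.
- 8.3.3.3 judges expectedness partly on how often an event occurs, which needs a numerator and a denominator.
- 10.1.6 needs safety data split by arm.

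The only denominator that the plan offers is unsuitable for harms, because finishing all sessions is a condition of entry. If an analyst used it by default, people who stopped because of an event would be missing.

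What is at stake is the pilot's conclusion on tolerability. Sections 2.2 and 4.3 describe the preliminary trials of this intervention as being in healthy adults. Section 9.2 says the pilot is meant to develop the intervention in older adults before a larger trial. Without a pre-specified summary, which harms are reported, and over which denominator, would be decided after the data are seen.

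**Working it through.** **Inputs.** 40 recruited, 10% dropout, 36 completing (5.5). Two arms with balanced totals (4.1). No allocation ratio is stated, so 20 per arm is an assumption. Those randomised but never treated may be replaced (7.2), so the number randomised could slightly exceed 40.

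**Step 1: the plan's own figure.** 40 × (1 − 0.10) = 36, which reproduces the stated number of completers. Before any loss to unusable data, the 9.3 set is therefore expected to hold 36 of 40, or 18 per arm if losses are equal.

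**Step 2: who is outside the 9.3 set.** Stopping the intervention because of an event means not completing 10 sessions. Everyone with that outcome fails the entry condition, so within this set the rate of discontinuation due to an event is 0 whatever the true rate. Participants who had an event but finished with usable data stay in.

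**Step 3: what zero events would mean.** The exact two-sided 95% upper limit for 0 of n is 1 − 0.025^(1/n); the one-sided limit is 1 − 0.05^(1/n).

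- n = 20: 1 − 0.025^(1/20) = 16.8% two-sided; 1 − 0.05^(1/20) = 13.9% one-sided.
- n = 18: 1 − 0.025^(1/18) = 18.5% two-sided.

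**Step 4: illustration of the denominator** (exact Clopper-Pearson limits; the event counts are hypothetical).

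| Stops due to an event in one arm | All randomised | Completers only |
|---|---|---|
| 2 | 2/20 = 10% (1.2% to 31.7%) | 0/18 (upper limit 18.5%) |
| 4 (all expected dropouts, 40 − 36) | 4/20 = 20% (5.7% to 43.7%) | 0/16 (upper limit 20.6%) |

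The right-hand column shows what the 9.3 set would give if it were used for harms. The plan does not propose that table.

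**Step 5: observation time.** Discontinued participants are left out of later assessments (7.1). If participation is taken to end on the day of stopping, someone who stops on Day 12 is covered for non-serious events to Day 12 + 7 = 19. A participant seen at Day 90 is covered to Day 90 + 7 = 97. For serious events the figures are 12 + 30 = 42 and 90 + 30 = 120. Simple proportions therefore cover unequal follow-up, and the table should say so.

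**The case against.** The strongest reply is that harms are not neglected. All events go on case report forms and into the study database (8.3.4, 10.1.9.1). Events are reported to the NIH and the IRB within 24 hours (8.3.5, 8.3.6). The randomization code is kept (6.3). The DSMB sees data by arm, with its data elements to be defined under a charter that is not among these documents. Section 10.1.11 says "results information from this trial will be submitted to ClinicalTrials.gov". All of this stands, and it rules out several stronger readings that a reader might infer:

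- *The trial cannot report harms by arm.* It can; the data and the allocation exist. What is missing is a pre-specified final summary.
- *The plan discards the records of people who stopped.* It does not. Their events are captured and followed. Section 9.3 is worded around the primary endpoints and never says that it governs event summaries.
- *The N/A is a deliberate decision to withhold harms.* The text does not show the intent. Section 8.2, Safety Assessments, is also N/A although 8.3 sets out full procedures.
- *This population has never been studied.* The reference list includes randomised mindfulness trials in subjective cognitive decline. Only the preliminary trials of this intervention are described as being in healthy adults.
- *The trial could test the statement of no known long-term risk in 2.3.1.* Follow-up to Day 90 and about 20 per arm cannot do that, as the limits in Step 3 show.

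What the reply does not answer is the gap itself. Individual reports and DSMB review are oversight, the registry sentence does not mention adverse events, and none of these fixes a denominator or a set of outcomes for the final report.

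**Conclusion.** The point holds as a gap in pre-specification. Followed as written, the plan yields no by-arm harms summary in the final analysis and defines no set that contains a participant who stopped before session 10 because of an event. Sections 9.4.4 and 9.3 need to be reconciled with 8.3.4 and 10.1.6. The efficacy analyses are not affected.

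The size is modest but relevant for a pilot. With an assumed 20 per arm, even a clean record would be compatible with an event proportion of up to 16.8% in an arm, so counts need intervals beside them. The choice of denominator alone could turn an observed 10% stopping rate into zero. The event counts are illustrations and not forecasts; the documents give no expected adverse event rate.

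**What to change.** - **In 9.3, add:** *Safety set: all randomised participants, analysed as allocated.* A set limited to people who attended a session would miss events at the baseline MRI, because 4.1 places randomisation before the baseline assessment and 8.3.3.2 attributes events to any study procedure.
- **In 9.4.4, replace N/A with:** *Number and percentage per arm with any AE, any SAE, any related AE, and intervention discontinuation due to an AE, with exact two-sided 95% confidence intervals; no hypothesis tests. Events between consent and randomisation are listed separately. The shorter AE observation time after early discontinuation is noted with the table.*
- **In 9.4.8,** allow for that short listing.
- **For the DSMB,** the same table can serve as the by-arm safety summary that 10.1.6 requires, so that oversight and final report share one denominator.

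The cost is one descriptive table from data already held and two sentences in the SAP, plus the listing and footnote. No data collection, sample size or clinical rule changes.

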8.3.5 ADVERSE EVENT REPORTING

In consultation with the PI, a trained member of the study team will be responsible for conducting an evaluation of an adverse event and shall report the results of such evaluation to the NIH and the reviewing Institutional Review Board (IRB) as soon as possible, but in no event later than 24 hours after the investigator first learns of the event.

8.3.6 SERIOUS ADVERSE EVENT REPORTING

In consultation with the PI, a trained member of the study team will be responsible for conducting an evaluation of a serious adverse event and shall report the results of such evaluation to the NIH and the reviewing Institutional Review Board (IRB) as soon as possible, but in no event later than 24 hours after the investigator first learns of the event.

8.3.7 REPORTING EVENTS TO PARTICIPANTS

The PI will be responsible for reporting AEs or SAEs related to the study to participants as soon as possible, but in no event later than 24 hours after the investigator first learns of the event.

For incidental findings from MRI brain scan, the MRI facility will inform the PI if there is incidental finding and the PI will report the finding to participants as soon as possible, but in no event later than 24 hours after the investigator first learns of the event.

8.3.8 EVENTS OF SPECIAL INTEREST

N/A

8.3.9 REPORTING OF PREGNANCY

N/A

8.4 UNANTICIPATED PROBLEMS

8.4.1 DEFINITION OF UNANTICIPATED PROBLEMS

This protocol uses the definition of Unanticipated Problems as defined by the Office for Human Research Protections (OHRP). OHRP considers unanticipated problems involving risks to participants or others to include, in general, any incident, experience, or outcome that meets all of the following criteria:

- Unexpected in terms of nature, severity, or frequency given (a) the research procedures that are described in the protocol-related documents, such as the Institutional Review Board (IRB)-approved research protocol and informed consent document; and (b) the characteristics of the participant population being studied;
- Related or possibly related to participation in the research (“possibly related” means there is a reasonable possibility that the incident, experience, or outcome may have been caused by the procedures involved in the research); and
- Suggests that the research places participants or others at a greater risk of harm (including physical, psychological, economic, or social harm) than was previously known or recognized.

8.4.2 UNANTICIPATED PROBLEMS REPORTING

The investigator will report unanticipated problems (UPs) to the reviewing Institutional Review Board (IRB) and to the Data Coordinating Center (DCC)/lead principal investigator (PI). The UP report will include the following information:

- Protocol identifying information: protocol title and number, PI's name, and the IRB project number
- A detailed description of the event, incident, experience, or outcome
- An explanation of the basis for determining that the event, incident, experience, or outcome represents an UP
- A description of any changes to the protocol or other corrective actions that have been taken or are proposed in response to the UP

To satisfy the requirement for prompt reporting, UPs will be reported using the following timeline:

- UPs that are serious adverse events (SAEs) will be reported to the IRB and to the DCC/study sponsor/funding agency within 10 business days of the investigator becoming aware of the event.
- Any other UP will be reported to the IRB and to the DCC/study sponsor/funding agency within 10 business days of the investigator becoming aware of the problem
- All UPs should be reported to appropriate institutional officials (as required by an institution's written reporting procedures), the supporting agency head (or designee), and the Office for Human Research Protections (OHRP) within 10 business days of the IRB's receipt of the report of the problem from the investigator.

8.4.3 REPORTING UNANTICIPATED PROBLEMS TO PARTICIPANTS

The PI will be responsible for reporting UPs related to the study to participants as soon as possible, but in no event later than 10 working days after the investigator first learns of the UP.

9 STATISTICAL CONSIDERATIONS

9.1 STATISTICAL HYPOTHESES

- Primary Endpoint(s):

We hypothesize that, compared to participants who receive a control intervention, participants who receive IBMT for improving behavior and cognition will have improved working memory, emotion regulation, and reduced subjective report of cognitive decline after completing the intervention at post-assessment, and will continue to show improvement 3 months after the intervention. Alternatively, our null hypothesis is that there will be no difference in the effects of IBMT for improving behavior and cognition and those of control intervention at post-assessment or after 3 months of intervention.

- Secondary Endpoint(s):

We hypothesize that, compared to participants who receive a RT control intervention, participants who receive IBMT for improving brain function and structure will have improved white matter, grey matter, and functional connectivity in AD-signature regions after completing the intervention at post-assessment, and will continue to show improvement 3 months after the intervention. Alternatively, our null hypothesis is that there will be no difference in the effects of IBMT for improving brain function and structure and those of RT at post-assessment or after 3 months of intervention.

